12.4.7. Plan for Missing Data

Several strategies will be imposed to minimize the impact of missing data on conclusions. Prevention is the most obvious and effective manner to control bias and loss of power from missing data (NRC 2010). This protocol will follow the intent to treat principle, requiring followup of all subjects randomized regardless of the actual treatment received (Lachin, 2000). The only reasons for not considering a subject in analyses will be withdrawal of consent, a false positive test for SARS-CoV-2, or lost to follow-up. The informed consent and protocol will distinguish between treatment discontinuation and study withdrawal and the consent will also include a statement about the importance of continuing data collection despite treatment discontinuation. Alternative contact information will be identified on entry into the study to minimize loss-to follow-up. Timely data entry combined with weekly missing data reports will trigger protocols for tracking and obtaining missing data items or outcome assessments. Despite these prevention efforts it is reasonable to assume missing data will occur. The primary analysis is valid under the assumption that missing data is missing at random (MAR). The plausibility of this assumption will be evaluated by determining the extent of missing data and using logistic regression to identify factors associated with dropout. While differential rates of dropout between groups or high loss to follow-up are not expected, sensitivity analysis using patternmixture and selection models under missing not at random (MNAR) assumptions will be performed to examine the robustness of conclusions of the primary analysis to missing data.

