12.3. Analysis Sets

12.3.1. Intention to Treat (ITT) Population

The intention-to-treat (ITT) population includes all participants randomized according to their initial randomized assignment regardless of the treatment actually received.

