12.3.2. Antiviral Efficacy Analysis Population

The antiviral efficacy analysis population will consist of all randomized participants with a baseline viral load $>10^5$ copies/mL.

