12.3.3. Per Protocol (PP) Population

The per-protocol (PP) population includes all ITT participants who did not have any major protocol deviations. The final determination of the exclusion of subjects from the PP population will be made prior to the database lock.

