The primary analysis will test whether the viral load in nasopharyngeal samples is lower at Day 4 in those receiving LAM-002A compared to placebo. All participants in the antiviral efficacy analysis set (i.e. the subgroup with baseline viral load >10⁵ copies/mL) will be included in the primary analysis. Viral load will be measured by a qRT-PCR test at Days 1 and 4. The analysis for the primary endpoint will focus on the log₁₀ viral RNA on Day 4. A repeated measures mixed model will be used to compare the two treatment groups. The mixed model will jointly model day 1 and day 4 viral load and will allow for the inclusion of all participants with at least one viral load assessment [Carpenter 2007]. The model will include fixed effects for treatment and age. Random effects will be included for subject and site. Linear contrasts will be used to compare the difference between groups for Day 4. This difference will be conditional on baseline viral load and is equivalent to an analysis adjusted for baseline [Carpenter 2007]. 95% CIs will be estimated for treatment differences at Day 4. A supportive analysis will be conducted using the ITT population, stratified by baseline viral load >10⁵ copies/mL vs. viral load ≤10⁵ copies/mL.

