12.4.4.1. Secondary Outcome: Hospitalization or Death Within 28 Days

The proportion of those progressing to hospitalization or death within 28 days of randomization will be compared between treatment groups using logistic regression (Ge 2011). All participants in the ITT population will be included in this analysis. Covariates in the analysis will include age. Site will be included as a random effect. The risk difference and 95% confidence interval will be estimated. Supportive analysis of this outcome will use the antiviral efficacy analysis population and the PP population.

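### Section 12.4.7 drops whole subjects for withdrawal of consent or loss to follow-up, which discards observed outcomes and conflicts with the analysis sets and the primary and progression analyses

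*Combined protocol and SAP*

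**What the plan says.** Section 12.4.7 adopts the intent-to-treat principle and then says: "The only reasons for not considering a subject in analyses will be withdrawal of consent, a false positive test for SARS-CoV-2, or lost to follow-up". It goes on to assume data are missing at random, to examine dropout, and to plan pattern-mixture and selection models under missing-not-at-random assumptions.

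Other sections set different rules for who is analysed:

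- **12.3.1:** the ITT population "includes all participants randomized according to their initial randomized assignment regardless of the treatment actually received".
- **12.3.2:** the "antiviral efficacy analysis population will consist of all randomized participants with a baseline viral load" above 10^5 copies/mL.
- **12.3.3:** the per-protocol set "includes all ITT participants who did not have any major protocol deviations", so it inherits the ITT definition.
- **12.4.3:** the primary mixed model "will allow for the inclusion of all participants with at least one viral load assessment". In addition, "A supportive analysis will be conducted using the ITT population, stratified by baseline viral load".
- **12.4.4.1** (hospitalisation or death within 28 days): "All participants in the ITT population will be included in this analysis".
- **13.6:** when a subject withdraws permission to use health information, data gathered before that point still enter the analysis.

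The primary swab is taken on Day 4, and section 8.6 runs follow-up to Day 28.

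**The concern.** The exclusion in 12.4.7 depends on something that happens after randomisation, and up to 24 days separate the primary measurement from the end of follow-up. A subject lost at Day 11 or Day 22 can have a complete Day 4 result and a documented hospitalisation, and the sentence removes both. If the chance of leaving is related to outcome, deleting those subjects can bias the comparison, more so if the relation differs between arms. The values are already in hand, so this loss is avoidable.

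The text also gives two instructions. An analyst following 12.4.7 and one following 12.3 and 12.4.3 would analyse different subjects, and nothing says which section prevails.

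**Working it through.** **1. The passages side by side.** Take a subject with baseline above 10^5 copies/mL and a Day 4 swab, hospitalised on Day 9 and lost on Day 15.

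| Section | Is the subject analysed? |
|---|---|
| 12.3.1, 12.3.2 | Yes, in both sets |
| 12.4.3 | Yes, with both viral loads |
| 12.4.4.1 | Yes, as an ITT participant |
| 12.4.7, missing-not-at-random models | Yes; these models need dropouts kept in the data |
| 12.4.7, exclusion sentence | No |

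**2. The plan's own sample size.** Inputs from 12.2: d = 0.60, two-sided alpha 0.20, power 90%, 142 enrolled, 10% loss. Power is taken from the noncentral t with N − 2 degrees of freedom and noncentrality d × √(N/4).

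- N = 74 gives 0.901, so the stated 37 per group reproduces.
- With N = 142 × 0.9 × subgroup proportion, power is 0.801, 0.865, 0.908, 0.939, 0.959, 0.973 and 0.982 for proportions 0.40 to 1.00. The table gives 0.79, 0.86, 0.91, 0.94, 0.96, 0.97 and 0.98.

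**3. Power cost of dropping the lost subjects.**

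- 50% in the subgroup: 142 × 0.5 = 71 gives 0.891; 71 × 0.9 = 63.9 gives 0.865. Difference 0.026.
- 40% in the subgroup: 56.8 gives 0.832; 51.1 gives 0.801. Difference 0.031.

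This is an upper limit, because it assumes every lost subject had a Day 4 value. The 12.2 table already deducts the 10%.

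**4. Bias in the Day 4 comparison.** The loss pattern is assumed. There is no drug effect and R-squared is 0, as in 12.2. The test is a pooled t-test at two-sided 0.20. Subjects are deleted after Day 4 with weight exp(b × Day 4 value in SD), so b = 0.5 and b = 1 mean the chance of loss rises 1.65-fold and 2.72-fold per SD. Each row rests on 40,000 or 100,000 simulated trials. Negative bias favours the drug.

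| Loss pattern | Deleted (active; placebo) | Bias, SD | Type I error |
|---|---|---|---|
| Unrelated to outcome | 4 of 36; 3 of 35 | about 0 | 0.200 |
| Both arms, b = 0.5 | 4 of 36; 4 of 36 | about 0 | 0.206 |
| Both arms, b = 1 | 4 of 36; 4 of 36 | about 0 | 0.219 |
| Active arm only, b = 0.5 | 4 of 36; 3 of 35 | −0.057 | 0.210 |
| Active arm only, b = 1 | 4 of 36; 3 of 35 | −0.107 | 0.248 |
| Active arm only, b = 1 | 2 per arm | −0.051 | 0.215 |

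With all observed values kept, bias is within 0.002 SD and type I error is 0.196 to 0.203. The effect used for sample size is 0.6 SD.

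**5. Progression.** Assume 71 per arm and 7 true events per arm, and let x hospitalised subjects in one arm leave later and be dropped. The risk difference becomes (7 − x)/(71 − x) − 7/71: −1.3, −2.6 and −4.0 percentage points for x = 1, 2 and 3. Equal deletion in both arms moves it by 0.

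**6. Does counting events before loss suffice?** Assume true risk r = 0.10, loss proportion L unrelated to outcome, and half of lost subjects' events recorded before loss. If event-free lost subjects are treated as missing and removed, the estimated risk is [r(1 − L) + 0.5rL] / [(1 − L) + 0.5rL].

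- L = 0.05: 0.0975/0.9525 = 10.2%.
- L = 0.15: 0.0925/0.8575 = 10.8%.

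The estimate is inflated in both cases. Unequal loss (5% in one arm, 15% in the other) would create a spurious difference of about 0.55 points.

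**The case against.** The strongest defence is that one loosely worded general sentence stands against several specific ones that agree with each other. Section 12.4.3 sets its own inclusion rule for the primary endpoint, and 13.6 keeps data collected before withdrawal. The neighbouring sentences in 12.4.7 deal with treatment discontinuation, so the likely purpose was to say that stopping treatment is no ground for exclusion. Full methods are deferred to a SAP.

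Much of this stands: for the primary endpoint the observed value is largely protected. Three parts do not settle the matter. Section 13.6 concerns permission to use health information, which is close to consent to participate but not the same. The reading that the sentence merely explains why data may be absent is weak, because the same list names false-positive subjects, who can have complete data. And 12.4.4.1 has no inclusion rule of its own beyond the ITT definition that 12.4.7 undercuts.

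It is also fair that lost hospitalisations should be uncommon: they are generally serious adverse events, and 9.6 and 9.7.1 require follow-up of those. But 9.6 exempts subjects who withdraw consent for follow-up, one of the two groups that 12.4.7 removes.

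A reader might infer that 12.4.7 also contradicts its own plan for "using logistic regression to identify factors associated with dropout". It does not: that regression is a diagnostic and can be run on all randomised subjects whatever the efficacy analysis includes. Only the missing-not-at-random models conflict with the exclusion.

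**Conclusion.** Wrong as written: followed literally, the rule discards outcomes already observed after randomisation, and it conflicts with the sections that define who is analysed. It should be corrected, but its likely effect is modest.

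The size depends on loss patterns that the documents do not give. Power cost is at most about 0.03. With about 7 of 71 subjects deleted after Day 4 and no drug effect:

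- **Loss unrelated to outcome:** bias is 0.
- **Outcome-related equally in both arms, equal numbers deleted:** bias is about 0, with type I error within about 0.20 to 0.23, allowing for simulation set-up.
- **Outcome-related in the active arm only:** bias is 0.06 to 0.11 SD, with type I error 0.21 to 0.25. With only 2 deletions per arm the worse case falls to about 0.05 SD and 0.21 to 0.22.

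Two stronger conclusions are tempting and not supported. A reader might infer that the primary result is seriously biased; 12.4.3 argues against that, the active-arm-only mechanism is an assumption, and 12.4.7 itself expects no differential dropout. A reader might also infer bias of 0.01 to 0.02 SD even when outcome-related loss is the same in both arms. That figure arises from deleting unequal numbers (4 of 36 against 3 of 35) and disappears when 4 of 36 are deleted from each arm.

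**What to change.** In 12.4.7, delete withdrawal of consent and loss to follow-up as subject-level exclusions and add text such as:

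> Within each analysis set, all data observed up to withdrawal or last contact are analysed in the assigned arm; only later values are treated as missing.

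For 28-day hospitalisation or death, count every event recorded before loss. Handle event-free subjects with unknown Day 28 status by a pre-specified method that uses their follow-up to last contact, for example multiple imputation under missing at random or a time-to-event estimate of 28-day risk. Do not delete them as incomplete cases (working, step 6). Add a sensitivity analysis.

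As a separate, smaller point, make the false-positive exclusion and 12.3.1 agree. Either keep those subjects in the ITT set or write the exclusion into its definition, decided from pre-dose samples and blind to arm. This mainly touches the ITT analyses, since a false-positive subject would not be expected to exceed 10^5 copies/mL at baseline.

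Carry the same text into the SAP before database lock. Sample size, visits and data collection do not change. The cost is the rewording plus a little more analysis work for the progression endpoint.

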12.4.8. Safety and Tolerability Analyses

Adverse events (AEs) and serious adverse events (SAEs) will be categorized by severity and relation to study drug using the Safety population. AEs will be classified according to the National Cancer Institute Common Terminology Criteria for Adverse Events, version 5.0.

Safety endpoints including SAEs, Grade 3 and 4 adverse events and signs compatible with cardiac arrhythmias, allergic reactions, gastrointestinal, hepatobiliary, eye and ear, blood and lymphatic system disorders and acute exacerbation of lung disorders will be described by treatment group. Each AE will be counted once for a given participant and graded by severity and relationship to COVID-19 or study intervention. AEs will be presented by system organ

class, duration (in days), start- and stop-date. Adverse events leading to premature discontinuation from the study intervention and serious treatment-emergent AEs will be presented in tables and listings.

Differences between treatment groups for safety outcomes will be tested at the 0.05 (2-sided level of significance) without correction for multiple testing.

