4.2. Secondary Endpoints

4.2.1. Safety and Tolerability

• The proportion of LAM-002A-treated subjects who develop TEAEs compared to placebo.

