5. STUDY DESIGN AND CONDUCT

5.1. Study Design

This is a double-blind, randomized, placebo-controlled Phase II study for the treatment of SARS-CoV-2 positive outpatient individuals with LAM-002A. The study will compare the active arm of LAM-002A plus standard of care, with the control placebo arm plus standard of care. This study will be conducted in approximately 142 adult subjects ages ≥ 18 , with ≤ 8 days of symptom onset, who are SARS-CoV-2 positive as determined by a validated test. The study will enroll subjects who have at least one of the following COVID-19-related symptoms indicating mild disease: fever (temperature ≥ 100.4), anosmia (loss of taste or smell), cough, sore throat, gastrointestinal complaints (e.g. nausea, vomiting or diarrhea), chills, congestion or runny nose, headaches, muscle or body aches, fatigue, without shortness of breath or dyspnea (RR<20, SpO2 >93% on room air), or asymptomatic patients who have tested positive for COVID-19 via a validated test within the past 4 days. Subjects will be treated with 125 mg LAM-002A PO, BID, or with placebo PO, BID for 10 days (20 doses). The treatment schedule is outlined in the Schedule of Activities (SoA), Table 1. Subjects will be followed at 4, 6, 8, 11, 22 and 28 days after the treatment start.

Subjects will be randomized using a permuted block scheme (with variable block size) in a 1:1 ratio to one of the two groups: (1) LAM-002A, or (2) placebo. To assure at least 71 placebo participants have a viral load $\ge 2 \times 10^3$ copies/mL (the lower limit of detection of the assay) at Day 4, 142 participants with baseline viral load $\ge 10^5$ copies/mL will be enrolled to achieve the primary objective; thus, an expected 142 subjects will be randomized (71 to receive LAM-002A and 71 to receive placebo). Because the existing longitudinal data on viral load in subjects are preliminary, this baseline viral load and number of participants randomized may be adjusted to allow for 71 placebo participants above the lower limit of detection of the assay ($\ge 2 \times 10^3$ copies/mL) at Day 4 so that a difference in viral clearance between the groups can be assessed.

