9.1.4. Treatment-Emergent Adverse Event

A TEAE is defined as an AE that occurs or worsens in the period from the first dose of study drug administration to Day 28 of the study.

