12.3.4. Safety Population

The safety population will include all randomized subjects who received at least one dose of the study drug.

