12.4. Statistical Analyses

12.4.1. General Considerations

This is a double-blind placebo controlled randomized trial testing the superiority of LAM-002A compared to placebo for Day 4 viral load at the two-sided overall type I error rate of 0.20. Secondary hypotheses will be described according to the appropriate summary statistics (e.g., proportions for categorical data, means with 95% confidence intervals for continuous data, median for time-to-event data). Diagnostic tests and sensitivity analyses will be performed. Parametric distributional assumptions will be checked. If assumptions fail, other distributions will be considered prior to transformations and non-parametric methods for sensitivity analysis. A statistical analysis plan (SAP) will be developed and filed with the study sponsor prior to database lock.

12.4.2. Comparability of Baseline Characteristics.

Distributions of baseline demographic and clinical characteristics will be summarized by intervention group. Comparability for continuous variables will be examined graphically and by summary statistics (means, medians, quartiles, etc.). Categorical variables will be examined by calculating frequency distributions. No inferential statistics will be calculated.

12.4.3. Analysis of Primary Outcome: Viral Load in Nasopharyngeal Samples at Day 4

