12.4.8.1. Adverse Events

Treatment-emergent AEs and non-TEAEs (those occurring prior to administration of study medication or that first occurred prior to study drug administration and did not worsen in frequency or severity) will be listed. TEAEs will be defined as AEs that occur on or after the date and time of study drug administration, or those that first occur pre-dose but worsen in frequency or severity after study drug administration. AEs will be followed-up until complete resolution, or until the PI or Sub-Investigator judges safe to discontinue follow-up.

The incidence of TEAEs will be summarized using the safety population. The MedDRA® dictionary Version 23 will be used to classify all AEs reported during the study by system organ class (SOC) and preferred term (PT). Incidence of subjects who experienced TEAEs will be presented by treatment and overall, SOC, PT, by Investigator-assessed relationship and also by severity. Each subject may only contribute once to each of the incidence rates, for a TEAE following a given treatment, regardless of the number of occurrences; the highest severity or highest relationship will be presented, as appropriate. In each table, SOC will be presented in descending order of overall incidence rate in terms of frequency of subjects and then in frequency of events (alphabetical order will be used in case of equal rates). For each SOC, PT will be presented the same way.

Incidence of TEAEs (number of events) will also be presented by treatment and overall, by SOC, and PT, by Investigator-assessed relationship and severity.

Severity of AEs will be rated according to CTCAE criteria as outlined in Section 9.4 and defined in Table 3 as Grade 1 (mild), Grade 2 (moderate), Grade 3 (severe), Grade 4 (life-threatening) and Grade 5 (fatal).

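### The final safety comparison rests on an unnamed 0.05 test with no risk difference or confidence interval, so a non-significant result will not show how large an excess remains possible

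*Combined protocol and SAP*

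**What the plan says.** Safety is a secondary endpoint, and Section 4.2.1 defines it comparatively: "The proportion of LAM-002A-treated subjects who develop TEAEs compared to placebo". TEAEs count "from the first dose of study drug administration to Day 28 of the study" (Section 9.1.4). The safety population is everyone randomized who took at least one dose (Section 12.3.4).

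The analysis text does three things:

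- Section 12.4.8 lists groups of safety outcomes, ending with "blood and lymphatic system disorders and acute exacerbation of lung disorders will be described by treatment group".
- Section 12.4.8 then adds the comparison rule: "Differences between treatment groups for safety outcomes will be tested at the 0.05 (2-sided level of significance) without correction for multiple testing". It does not name the test.
- Section 12.4.8.1 sets out the tables: "Incidence of subjects who experienced TEAEs will be presented by treatment and overall, SOC, PT, by Investigator-assessed relationship and also by severity".

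Section 12.4.1 gives the general rule that "Secondary hypotheses will be described according to the appropriate summary statistics". For categorical data it mentions only proportions; the 95% interval it mentions is for means of continuous data.

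No part of Sections 12.4.8 to 12.4.9 plans a between-arm risk difference, risk ratio or interval for a safety outcome. Section 12.4.4.1 does plan a risk difference with a 95% confidence interval for hospitalization or death, which is also a binary secondary endpoint.

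**The concern.** A safety analysis should show how large an excess of harm the data leave open. A test at 0.05 answers a different question. In a trial sized for viral load, it will often be non-significant for adverse events that are uncommon or only moderately increased. Without an interval, such a result carries no statement of uncertainty, and a reader may take it as reassurance.

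Section 2.3 says that no one with COVID-19 had been treated and that risk and benefit in this disease are not understood. Section 5.3 expects the trial to inform Phase III. Those planning the next trial will need an upper limit on the excess as well as a p-value.

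**Working it through.** **Inputs from the protocol.** 71 per arm (Section 5.1); two-sided 0.05, uncorrected (Section 12.4.8). GI event rates at 125 mg BID in the earlier lymphoma study: nausea 35.9%, vomiting 25.6%, diarrhea 25.6% (Section 5.4).

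**Assumptions.** The documents give no placebo event rates, so every placebo rate below is assumed. All 71 per arm are taken as dosed. Because the test is unnamed, both Fisher's exact test and the uncorrected chi-square test are shown.

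**The plan's own figure.** No power is stated for safety. The stated sample size is for viral load (Section 12.2: Cohen's d 0.60, two-sided 0.20, power 90%):

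n per arm = 2(1.2816 + 1.2816)² / 0.60² = 2 × 6.570 / 0.36 = 36.5, so 37 per arm and 74 in total.

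This matches the protocol. It also shows that the trial's size was not chosen with adverse events in mind.

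**Power of the safety test.** For each pair of true rates, power is the sum of the binomial probabilities of all outcomes (a of 71 on placebo, b of 71 on LAM-002A) with p ≤ 0.05 and more events on LAM-002A.

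| Placebo v LAM-002A | Fisher | Chi-square |
|---|---|---|
| 1% v 5% | 8% | 26% |
| 2% v 10% | 37% | 55% |
| 5% v 15% | 41% | 53% |
| 10% v 20% | 31% | 39% |
| 10% v 30% | 82% | 87% |
| 5% v 25.6% | 93% | 95% |
| 10% v 35.9% | 95% | 97% |

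The first four rows are uncommon or moderate increases, and the last three are large ones. The last two use the protocol's own GI rates on the active side.

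**What an interval adds.** Take 11/71 on LAM-002A and 4/71 on placebo.

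- Rates: 15.49% and 5.63%; difference 9.86 points.
- Fisher p = 0.099. Chi-square: pooled rate 15/142 = 0.1056, SE = √(2 × 0.1056 × 0.8944 / 71) = 0.0516, z = 0.0986 / 0.0516 = 1.91, p = 0.056. Neither is significant.
- Wilson 95% limits: 8.88% to 25.65% for 11/71, and 2.21% to 13.61% for 4/71.
- Newcombe lower limit: 9.86 - √[(15.49 - 8.88)² + (13.61 - 5.63)²] = 9.86 - 10.36 = -0.5 points.
- Newcombe upper limit: 9.86 + √[(25.65 - 15.49)² + (5.63 - 2.21)²] = 9.86 + 10.72 = 20.6 points.

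Two further examples by the same method:

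- 14/71 v 7/71: 9.9 points (-2.0 to 21.7), Fisher p = 0.15.
- 7/71 v 4/71: 4.2 points (-5.2 to 14.0), Fisher p = 0.53.

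All three are non-significant, yet the upper limits run from 14 to 22 points.

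**The case against.** **Safety is not judged by tests alone.** A reader might infer that it is. The protocol also describes outcomes by arm, tabulates TEAE incidence by organ class, preferred term, severity and relationship (12.4.8.1), gives laboratory summaries and shifts (12.4.8.2), has the DSMB review events throughout (5.2), and sets a death boundary at 15 per arm (12.5). With per-arm counts, anyone can work out a difference and an interval. This stands. What remains is that the planned analysis does not itself report them.

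**The test does not miss most real increases.** Power depends on assumed rates, and the increases most expected with this drug are gastrointestinal. If placebo rates are 5% to 10%, increases to the rates seen earlier would often be detected, as the table shows. Nor can one say that a tripling would usually be missed: 5% v 15% has 41% or 53% power depending on the test, and 10% v 30% has 82% or 87%. This stands and limits the point to uncommon or moderate increases.

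**The missing multiplicity correction is not the fault.** It is openly stated and defensible for safety; correction would lower power further. One might compute 1 - 0.95⁹ = 37% as the chance of a false alarm over the nine groups listed in 12.4.8. That figure needs nine independent tests, each at the full 5%. The groups overlap, since serious and Grade 3-4 events cut across organ systems, and the text does not say that exactly nine tests are run. Fisher's actual size at 71 per arm is about 0.15%, 1.4% and 2.6% at event rates of 2%, 5% and 10%, so nine independent Fisher tests would give about 1%, 12% and 21%.

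**Sections 12.4.1 and 12.4.8 are not in clear conflict.** Section 12.4.1 is a general statement, 12.4.8 both describes and tests, and other secondary endpoints are also modelled. Nothing in 12.4.8 says that non-significance will be read as no difference.

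**A later SAP may add intervals.** Sections 12 and 12.4.1 defer full detail to an SAP filed before database lock. That is the natural place for the change, but the present text commits only to the test.

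**Conclusion.** The point holds as a modest one about estimation. The final safety analysis plans a significance test and no measure of the between-arm difference or its uncertainty, although the protocol plans both for hospitalization or death. At 71 per arm, Fisher power is between 8% and 41% (chi-square 26% to 55%) for the uncommon or moderate increases examined, and a non-significant result can sit beside an upper limit of 14 to 22 points. These figures rest on assumed placebo rates, on all 71 per arm being dosed, and on example counts chosen for illustration. The documents do not support a claim that the safety analysis as a whole is inadequate or that large increases would go unseen. This is a cheap improvement and does not threaten the trial's conclusions.

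**What to change.** In Section 12.4.8, and in the SAP, replace the testing sentence with wording such as:

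*For the proportion of subjects with TEAEs and for each listed safety outcome, the risk difference (LAM-002A minus placebo) will be reported with a two-sided 95% confidence interval (Newcombe). Any p-values are unadjusted and descriptive, the test used will be named, and a non-significant result will not be interpreted as absence of harm.*

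The cost is a wording change and a few extra columns in the safety tables. No new data, visits or subjects are needed, and the per-arm tables and DSMB review stay as they are.
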